## **STATEMENT OF COMPLIANCE**

Each engaged institution must have a current Federal-Wide Assurance (FWA) issued by the Office for Human Research Protections (OHRP) and must provide this protocol and the associated informed consent documents and recruitment materials for review and approval by an appropriate Institutional Review Board (IRB) or Ethics Committee (EC) registered with OHRP. Any amendments to the protocol or consent materials must also be approved before implementation.

The trial will be carried out in accordance with International Conference on Harmonisation Good Clinical Practice (ICH GCP) and the following:

- United States (US) Code of Federal Regulations (CFR) applicable to clinical studies (45 CFR Part 46, 21 CFR Part 50, 21 CFR Part 56, 21 CFR Part 312, and/or 21 CFR Part 812)

National Institutes of Health (NIH)-funded investigators and clinical trial site staff who are responsible for the conduct, management, or oversight of NIH-funded clinical trials have completed Human Subjects Protection and ICH GCP Training.

The protocol, informed consent form(s), recruitment materials, and all participant materials will be submitted to the Institutional Review Board (IRB) for review and approval. Approval of both the protocol and the consent form must be obtained before any participant is enrolled. Any amendment to the protocol will require review and approval by the IRB before the changes are implemented to the study. In addition, all changes to the consent form will be IRB-approved; a determination will be made regarding whether a new consent needs to be obtained from participants who provided consent, using a previously approved consent form.

## 1 PROTOCOL SUMMARY

### 1.1 SYNOPSIS

**Title:** **A Phase II Study Evaluating Fostamatinib for Hospitalized Adults with COVID-19**

**Study Description:** This is a randomized, double-blind, placebo-controlled trial of fostamatinib for the treatment of hospitalized patients with COVID-19.

We will randomly assign fostamatinib or matched placebo (1:1) to approximately 60 eligible COVID-19 patients who are a 5 to 7 on the 8-point scale (requiring supplemental oxygen via nasal canula or non-invasive ventilation, requiring mechanical ventilation or extracorporeal membrane oxygenation).

**Objectives:** The primary objective of this study is to evaluate the safety of fostamatinib for the treatment of hospitalized patients with COVID-19.

Secondary objective will be to assess the early efficacy and clinically relevant endpoints of disease course

Exploratory objective will be to study the host immunological response to COVID-19 and potential mechanism of action of fostamatinib

**Endpoints:** The primary endpoint is cumulative incidence of SAEs through day 29.

Secondary endpoints are:

1. Time to recovery: day of recovery is defined as the first day on which the subject satisfies one of the following three categories by Day 29:  
Ordinal scale 3: hospitalized, not requiring supplemental oxygen-no longer requiring ongoing medical care;  
Ordinal scale 2: non-hospitalized, limitations on activities and/or requiring home oxygen  
Ordinal scale 1: non-hospitalized, no limitations on activities
2. Number of days free of mechanical ventilation [patients with baseline ordinal scale 5-6 only]
3. 14-day and 28-day mortality
4. Grade 3 and 4 AE through day 60.
5. Days of hospitalization
6. Ordinal scale at day 15 and day 29

7. Change in CRP, IL-6, d-dimer, ferritin, fibrinogen, absolute lymphocyte count, absolute neutrophil count, and platelet count from baseline [day 3, 5, 8, 11, 15, 29]
8. Number of days in the ICU [entire hospitalization]
9. Relative change in PaO2/FiO2 or SpO2/FiO2 ratio
10. Change in SOFA score from baseline (day 1) [day 3, 5, 8, 11, 15, 29]
11. Number of days on oxygen (Including nasal canula, non-invasive, and mechanical ventilation)
12. Days free of renal failure [entire hospitalization]
13. Clinically relevant deep vein thrombosis (DVT) or pulmonary embolism (PE) [entire hospitalization]

**Study Population:**

This trial is intended to enroll hospitalized patients with COVID-19, who are at least 18-years old requiring supplemental oxygen via nasal canula or non-invasive mechanical ventilation (5 or 6 on the 8-point scale) or on mechanical ventilation or ECMO (7 on the 8-point scale).

**Phase:**

Phase 2

**Description of Sites/Facilities Enrolling Participants:**

This will be a multicenter study. Enrollment will take place at the NIH Clinical Center and Inova health system hospitals with the potential of expanding to a 3rd site. We will enroll a total of approximately 60 evaluable patients . The study will be conducted exclusively in the United States.

**Description of Study Intervention:**

The study intervention is fostamatinib, an inhibitor of spleen tyrosine kinase that will be administered orally at a dose of 150 mg twice daily for 14 days or 28 doses. Subjects will receive standard of care and be randomized to receive fostamatinib or matching placebo.

**Study Duration:**

[figure not shown]
This study will enroll over 2-3 months and it will take another 1 month for data analysis.

**Participant Duration:**

An individual subject will complete the study in a maximum of 60 days, from screening at Day -1 or 1 to follow-up through Day 60 ± 3 days.

1.2 SCHEMA

*Abbreviated Title: Fostatinib for COVID*

*Version Date: 09/17/2020*

**1.3 SCHEDULE OF ACTIVITIES (SOA)**

Study Day	-1	1 h	2	3	4	5 d , f	6	7	8 d , f	9	10	11 d , f	12	13	14	15 c,d,f	Daily until day 15 if discharged on study drug or daily if in hospital until day 60	22 c,d,f	29 c,d,f	60 c,d,f
Informed Consent	X b	X b																		
Inclusion/exclusion	X b	X b																		
SARS-CoV-2 Test	X b	X b																		
Pregnancy Test	X b	X b																		
Medical History	X b	X b																		
Randomization		X																		
Adverse event evaluation		X	X	X	X	X	X	X	X	X	X	X	X	X	X	X	X k	X	X	X
Vital signs a	X	x	x	x	x	x	x	x	x	x	X	x	x	x	x	x i	x i	x i	x i	x i
Physical Exam/Review of symptoms	X b	X b																		
BMI Measurement	X																			
Ordinal Score		X	X	X	X	X	X	X	X	X	X	X	X	X	X	X	X	X	X	X
SOFA Score		X		X		X			X			X				X		X	X	

Template version date 12-11-2019

*Abbreviated Title: Fostatinib for COVID*

*Version Date: 09/17/2020*

Chest x-ray	X b	X b																		
Safety labs: CBC, BMP, LFTs j	X	x		x		x			x			x				x i		x i	x i	x i
Study drug		x	x	x	x	x	x	x	x	x	x	x	x	x	x					
Research bloods		x e		x e		x e			x e			x e				x e,i		x e,i	x e,i	x e,i
Oropharyngeal swab for viral RNA		x e		x e		x e			x e			x e				x e,i		x e,i	x e,i	x e,i

- a) Vital signs include temperature, systolic blood pressure, heart rate, respiratory rate, and O2 saturation
- b) Can be done on day prior or day of enrollment, except SARS-CoV-2 test which can be done up to 7 days prior.
- c) If still in hospital phone visit not required. If discharged assess for adverse events, clinical status on ordinal scale, readmission, and mortality. Can be performed while in hospital, done as outpatient visit, or via telehealth if subject unable to travel for any reason.
- d) Can be performed +/- 2 days from scheduled visit
- e) Outpatient visit can be +/- 3 days from scheduled visit for days 5, 8, 11, 15, 22, 29, 60 as applicable
- f) Following discharge patients only required to return for day 15, 22, 29, and 60 follow up visits unless they are discharged on study drug in which they will receive daily phone calls and will be required to have safety labs drawn as scheduled on days 3, 5, 8, 11 as applicable
- g) Day 1 is the first day of study drug
- h) Outpatient visits on day 5, 8, 11, 15, 22, 29, and 60 visits are preferred as in-person visits but may be done via telehealth and there is no need for vital signs or scheduled sample collection when telehealth is utilized unless outpatient labs can be requested via outside source (example Quest). Subjects with LFTs above 3x the ULN at enrollment will have LFTs checked daily during the hospitalization phase of the study.
- i) Outpatient adverse event monitoring will be performed via phone call
- j) Inpatient assessments will be done at the initial site of patient enrollment (NIH Clinical Center or Inova Health Systems.) After patient discharge, all outpatient assessments will be done at NIH Clinical Center, however laboratory can be done at non-NIH facility of patients who are having a telephone assessment.

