## 3 OBJECTIVES AND ENDPOINTS

The primary objective of this study is to evaluate the safety of fostamatinib for the treatment of hospitalized patients with COVID-19.

OBJECTIVES	ENDPOINTS	JUSTIFICATION FOR ENDPOINTS
Primary		
To assess the safety of fostamatinib in hospitalized patients with COVID-19	Cumulative incidence of SAEs through day 29.	This endpoint was chosen to evaluate the safety of fostamatinib for the treatment of hospitalized patients with COVID-19.
Secondary		

*Abbreviated Title: Fostamatinib for COVID*

*Version Date: 09/17/2020*

OBJECTIVES	ENDPOINTS	JUSTIFICATION FOR ENDPOINTS

To assess the effect of fostamatinib on clinically relevant endpoints of disease course
	
 
1. Time to recovery by day 29: day of recovery is defined as the first day on which the subject satisfies one of the following three categories: Ordinal scale 3: hospitalized, not requiring supplemental oxygen-no longer requiring ongoing medical care; Ordinal scale 2: non-hospitalized, limitations on activities and/or requiring home oxygen; Ordinal scale 1: non-hospitalized, no limitations on activities
 
2. Number of days free of mechanical ventilation [patients with baseline ordinal scale 5-6 only]
 
3. Mortality at day 14 and 28
 
4. Grade 3 and 4 AE through day 60
 
5. Days of hospitalization
 
6. Ordinal scale at day 15 and day 29
 
7. Change in CRP, IL-6, ferritin, d-dimer, fibrinogen, absolute lymphocyte count, absolute neutrophil count, and platelet count from baseline [day 3, 5, 8, 11, 15, 29]
 
8. Number of days in the ICU [entire hospitalization]
 
9. Relative change in PaO2/FiO2 or SpO2/FiO2 ratio
 
10. Change in SOFA score from baseline (day 1) [day 3, 5, 8, 11, 15, 29]
 
11. Number of days on oxygen (Including nasal canula, HFNC, non-invasive, and mechanical ventilation)
 
12. Days free of renal failure [entire hospitalization]
 
	
Each of the secondary clinical endpoints were deemed to be clinically relevant indicates for improved or worsening disease course

*Abbreviated Title: Fostamatinib for COVID*

*Version Date: 09/17/2020*

OBJECTIVES	ENDPOINTS	JUSTIFICATION FOR ENDPOINTS

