## 4 STUDY DESIGN

### 4.1 OVERALL DESIGN

We intend to study fostamatinib for the treatment of hospitalized patients with COVID-19.

- This will be a multicenter, randomized, double-blind, placebo-controlled, phase 2 trial with the objective to evaluate the safety of fostamatinib compared to matching placebo in COVID-19 patients who are hospitalized with a 5, 6, or 7 on the 8-point ordinal scale.
- The NHLBI will be the Coordinating Center for this multicenter study. All participating sites will enroll and treat subjects as described below. Research labs for exploratory endpoints will be processed at participating sites or shipped to the NIH Clinical Center for processing.
- All study participants will receive standard of care throughout the entire study and then will be randomized to 150 mg of fostamatinib twice a day or placebo for 14 days (total 28 doses).
- Subjects will be assessed daily while hospitalized and followed until day 60. If patients improve and are discharged prior to day 14 the study drug will be continued until day 14 as an outpatient. Patients who are discharged on study drug will receive a phone call daily to assess for adverse events and will have safety labs drawn on days 3, 5, 8, 11 as applicable (outpatient third party lab acquisition may be utilized as needed). We will make every effort to bring back discharged patients for outpatient visits on days 15, 22, 29, and 60 to include laboratory draws. In patients who are unable to follow-up, they will receive a telephone visit as a follow up.
- Day 1 of study is the first day of study drug and patients will be followed until day 60.

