4) Mortality rate and the time to event endpoints will be estimated by Kaplan-Meier method and 95% confidence intervals by study arm and compared between the treatment arms by log-rank test.

5) Longitudinal measurements of each biomarker variables will be plotted over time. The mean and percent change from baseline for each variable will be estimated and compared to study arm using appropriate parametric or nonparametric tests and regression modeling.

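### Footnote f, 4.1 and 8.3 conflict with footnotes e and h and 8.2.2 on whether research bloods are due after discharge on Days 5, 8 and 11, and 9.3.3 has no rule for the missing markers

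*Combined protocol and SAP*

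**What the plan says.** Footnotes are cited by their letter in the list under the Schedule of Activities (section 1.3).

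**The endpoint.** The synopsis lists "Change in CRP, IL-6, d-dimer, ferritin, fibrinogen, absolute lymphocyte count" among the markers. Section 3 completes the list and gives the days: "absolute lymphocyte count, absolute neutrophil count, and platelet count from baseline [day 3, 5, 8, 11, 15, 29".

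**Where the values come from.** In 8.2.2, fibrinogen and D-dimer (citrate), IL-6 (EDTA), and ferritin and CRP (lithium heparin) are research tubes sent to the NIH Clinical Lab. The safety labs in the schedule are CBC, BMP and LFTs, so they supply lymphocytes, neutrophils and platelets only.

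**Passages that require only safety labs after discharge.** Footnote f says: "Following discharge patients only required to return for day 15, 22, 29, and 60 follow up visits unless they are discharged on study drug". Patients discharged on study drug "will be required to have safety labs drawn as scheduled on days 3, 5, 8, 11 as applicable". Section 4.1 repeats those safety labs, allows a third-party lab, and adds: "We will make every effort to bring back discharged patients for outpatient visits on days 15, 22, 29, and 60 to include laboratory draws". Section 8.3 also names only daily calls and safety labs.

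**Passages that expect the research draw.** The Research bloods row is marked on Days 5, 8 and 11 with footnote e: "Outpatient visit can be +/- 3 days from scheduled visit for days 5, 8, 11, 15, 22, 29, 60 as applicable". Footnote h says: "Outpatient visits on day 5, 8, 11, 15, 22, 29, and 60 visits are preferred as in-person visits". It allows telehealth, and then waives scheduled samples unless an outside lab can be used. Section 8.2.2 lists the research tubes on Days 5, 8 and 11 with no inpatient limit.

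**The analysis.** Item 5 of 9.3.3 says: "The mean and percent change from baseline for each variable will be estimated and compared to study arm". It leaves the choice to suitable parametric or nonparametric tests and regression, and gives no rule for values missing because of discharge.

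**The concern.** Study drug continues to Day 14 after discharge, so going home on study drug is the normal path for anyone who recovers early. Under footnote f, 4.1 and 8.3, such a patient gives a CBC on Days 5, 8 and 11 but need not give the other five markers. Two sites reading different passages could collect different data.

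These values are not lost at random. Discharge moves a patient into ordinal categories 1 or 2, which count as recovery in the first-listed secondary endpoint, so missingness follows a good outcome. It also falls on treatment days, when an anti-inflammatory effect would be expected. If one arm is discharged sooner, the patients with its best marker response may leave the comparison first. Five markers would then describe mainly inpatients, while the three CBC markers describe nearly everyone. Values not drawn on those days cannot be recovered later.

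**Working it through.** **Step 1: who has what on Days 5, 8 and 11.**

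| Patient | Lymphocytes, neutrophils, platelets | CRP, IL-6, D-dimer, ferritin, fibrinogen |
|---|---|---|
| In hospital | yes | yes |
| Home on study drug, site follows f, 4.1, 8.3 | yes | not required |
| Home on study drug, site follows e, h, 8.2.2, in person | yes | yes |
| Home on study drug, telehealth, no outside lab | required by f | waived by h |

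Day 3 is little affected, because exclusion 3 removes patients expected to leave within 72 hours. Days 15 and 29 lie outside this conflict.

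**Step 2: size of the bias if discharged patients go unsampled.** The plan gives no discharge rates and no figure to reproduce; about 60 patients (30 per arm) is set by feasibility. The other inputs are assumptions. Let marker change have SD 1, with lower better, and let rho be its correlation with the severity that delays discharge. Patients below a severity threshold have gone home: a fraction q_s in the slower arm and q_f in the faster arm. With a = z(q) and λ(a) = φ(a)/(1 − Φ(a)),

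bias (faster minus slower arm) = rho × [λ(a_f) − λ(a_s)].

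Example, 30% v 50%: a_s = −0.524, λ = 0.497; a_f = 0, λ = 0.798. At rho 0.5 the bias is 0.5 × 0.301 = 0.151 SD against the faster arm.

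| Discharged, slower v faster | Inpatients of 30 | rho 0.3 | rho 0.5 | rho 0.8 | rho 1 |
|---|---|---|---|---|---|
| 10% v 20% | 27 v 24 | 0.046 | 0.077 | 0.124 | 0.155 |
| 20% v 35% | 24 v 20 | 0.066 | 0.110 | 0.176 | 0.220 |
| 30% v 50% | 21 v 15 | 0.090 | 0.151 | 0.241 | 0.301 |
| 50% v 70% | 15 v 9 | 0.108 | 0.181 | 0.289 | 0.361 |

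The bias is zero if rho = 0 or if q_s = q_f.

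**Step 3: against the standard error.** For 21 v 15 patients the SE is √(1/21 + 1/15) = 0.338 SD, so the bias is 0.27 to 0.89 SE. Selection also narrows the spread, to variance 1 − rho²λ(λ − a). At rho 0.8 this gives variances 0.675 and 0.593, SE √(0.675/21 + 0.593/15) = 0.268, and 0.241/0.268 = 0.90 SE. At rho 1 it gives 0.493 and 0.363, SE 0.218, and 1.38 SE. Only near-perfect correlation passes one SE in this row.

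**Step 4: shrink or reverse?** Observed difference = −(true benefit) + bias. With a benefit of 0.25 SD the sign turns in only three cells: 30% v 50% at rho 1 (+0.05), and 50% v 70% at rho 0.8 (+0.04) and rho 1 (+0.11). With 0.5 SD it never turns (−0.14 to −0.45 across the table).

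**Step 5: a second model.** Assume log-normal discharge times (log-SD 0.6, none before Day 3), medians Day 11 v Day 8, SD of log-marker change 0.8, and correlation 0.3/0.5/0.7. Unsampled after discharge: 9% v 22% on Day 5, 30% v 50% on Day 8, 50% v 70% on Day 11. With no marker effect, the Day 11 difference is +0.09/+0.15/+0.20 log units, about 0.3/0.5/0.75 SE. A true −0.40 appears as −0.31/−0.25/−0.20. With medians 11 v 7 and correlation 0.5 it appears as −0.19. With equal medians the bias is 0.00.

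**The case against.** The strongest reply is that the research draw is already scheduled. The Research bloods cells for Days 5, 8 and 11 carry an outpatient window, which would be pointless for inpatient-only draws. Footnote h prefers in-person visits and waives samples only in a narrow case. Section 8.2.2 has no inpatient limit. Footnote f sets a minimum for return visits and does not say that research bloods stop. This stands, so a reader who infers that the plan compares endpoint 7 only in patients still in hospital goes too far: that is one reading of passages that disagree. It does not remove the conflict, because f, 4.1 and 8.3 are the passages that say what is required of a discharged patient.

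A reader might also infer that the faster-recovering arm will look worse. Steps 4 and 5 do not support that. The usual result is attenuation, and a reversal needs a marker effect that is small or absent beside the effect on discharge. Deaths are left out of the calculation. They remove the sickest patients and, if they differ by arm, could offset or add to the bias.

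Nor does item 5 prescribe visit-by-visit tests on whoever was sampled. It speaks of longitudinal measurements and permits regression, so the fair criticism is that it is under-specified. Finally, Day 15 cannot be treated as a sample every discharged patient has: 4.1 promises effort, with a telephone visit otherwise.

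**Conclusion.** The conflict is in the text and does not depend on assumptions. Its consequence is conditional: five of eight markers, on three of six post-baseline days, in one of 13 secondary endpoints, may be missing because of discharge, and the analysis section does not say how to handle this. The direction, against the faster-discharged arm, needs both a difference in discharge timing and a correlation between marker fall and discharge. Under the assumed rates the bias is mostly below one standard error and usually shrinks a benefit.

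The gap does not reach lymphocytes, neutrophils or platelets in patients discharged on study drug, Days 15 and 29, or the primary endpoint. It is worth correcting because the correction is cheap and the lost samples cannot be replaced.

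**What to change.** 1. **Schedule.** Reconcile footnotes e, f and h with 4.1, 8.2.2 and 8.3. State that, for patients discharged on study drug, the endpoint 7 research tubes are drawn at the Day 5, 8 and 11 venipuncture already required for safety labs, in person or through the outside lab where feasible. The volume is 2 × 3 mL citrate + 3 mL EDTA + 4 mL lithium heparin = 13 mL per visit, already listed in 8.2.2.

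2. **Analysis.** In 9.3.3 item 5, specify one likelihood-based repeated-measures model of the log marker. Use all available visits, including Day 15 where sampled, with baseline marker and baseline severity as covariates. Report by arm and day the number discharged and unsampled, and the number who died. Label any inpatient-only summary as such.

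**Cost.** One schedule clarification, a few lines of analysis text, and some shipping. Some third-party draws (for example IL-6) may not reach the NIH lab; for those visits the model relies on a missing-at-random assumption, which the counts by arm help readers judge.

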## **7 STUDY INTERVENTION DISCONTINUATION AND PARTICIPANT DISCONTINUATION/WITHDRAWAL**

### **7.1 DISCONTINUATION OF STUDY INTERVENTION**

Study product administration for any given subject may be stopped for SAEs, clinically significant adverse events, severe laboratory abnormalities, or any other medical conditions that indicate to the Investigator that continued dosing is not in the best interest of the patient.

See section 6.1.2.3 for information on dosing modifications or discontinuation rules based on laboratory abnormalities or other adverse events.

Subjects who have the study product stopped for a safety related issues will not continue with dosing. In addition, subjects who have an allergic reaction that is temporally associated with study product administration and the PI believes it to be related to study product will not receive any more study product.

In addition, a subject in this clinical study may discontinue study drug at their request for any reason. Every effort should be made to encourage subjects to remain in the study for the duration of their planned outcome assessments. Subjects should be educated on the continued scientific importance of their data, even if they discontinue study drug.

Unless the subject withdraws consent, those who discontinue study drug early will remain in the study. The reason for subject discontinuation of study drug should be documented in the CRF.

Discontinuation from the study drug does not mean discontinuation from the study, and remaining study procedures should be completed as indicated by the study protocol. If a clinically significant finding is identified (including, but not limited to changes from baseline) after enrollment, the investigator or qualified designee will determine if any change in participant management is needed. Any new clinically relevant finding will be reported as an adverse event (AE).

The data to be collected at the time of study intervention discontinuation will include the following:

- Reason for discontinuation
- Date of last study drug administration
- Any adverse event
- Patients will be followed for clinical data required for the duration of the study

Participants are free to withdraw from participation in the study at any time upon request.

An investigator may discontinue a participant from study drug for the following reasons:

- Disease progression which requires discontinuation of the study intervention

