## **8.2 EFFICACY ASSESSMENTS**

For all baseline assessments and follow-up visits, refer to the Schedule of Assessments (SOA) for procedure to be done, and details below for each assessment.

Inpatient assessments will be done at the initial site of patient enrollment (NIH Clinical Center or Inova Health Systems.) After patient discharge, all outpatient assessments will be done at NIH Clinical Center either in person or remotely using NIH approved TeleMedicine software and approved NIH TeleMedicine guidance.

The subject's clinical status will be captured on each study day while hospitalized up until and including Day 60. If a subject is discharged prior to Day 15, clinical status is captured on Day 5, 8, 11, 15, 22, 29, and 60 if the subject returns for an in-person clinic visit or by phone or telehealth if an in-person visit is not possible. Clinical status will also be captured on Day 22 during a phone or telehealth visit. Clinical status is defined by secondary outcomes.

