### **8.2.2 Biospecimen Evaluations**

Research bloods will be sent from Inova hospitals to the NIH for processing in either the clinical laboratory -or- in a NHLBI research lab.

The amount of blood that may be drawn from subjects for research purposes shall not exceed 10.5 mL/kg or 550 mL, whichever is smaller, over any eight-week period.

*Abbreviated Title: Fostamatinib for COVID*

*Version Date: 09/17/2020*

Test/assay	Volume blood (approx.)	Type of tube	Frequency****	Location of specimen analysis
Routine* 
 
• CBC
 
• BMP
 
• Hepatic
 
	3 mL  4 mL	EDTA tube (lavender)  Lithium Heparin tube (light green)	Baseline (prior to enrollment)  D1-entire hospitalization, D15, D22, D29, D60 if outpatient	Clinical Lab  At participating sites
Research* 
 
• PT
 
• PTT
 
• INR
 
• Fibrinogen
 
• D-dimer
 
• Von Willebrand factor
 
	3 ml x2	Sod Citrate (BLU) x2	D1, 3, 5, 8, 11, 15, 22, 29, 60	NIH Clinical Lab
Research* 
 
• P-selectin
 
• Thrombomodulin
 
	3 ml	Sod Citrate (BLU)	D1, 3, 5, 8, 11, 15, 22, 29, 60	NIH Clinical Lab
Research* 
 
• IL-6
 
	3mL	EDTA (lavender)	D1, 3, 5, 8, 11, 15, 22, 29, 60	NIH Clinical Lab
Research* 
 
• Ferritin
 
• CRP
 
	4 mL	Lithium Heparin tube (light green)	D1, 3, 5, 8, 11, 15, 22, 29, 60	NIH Clinical Lab
Research (exploratory) 
 
• Serum tube
 
	8 mL	Serum Separator Red top tube	D1, 3, 5, 8, 11, 15, 22, 29, 60	NHLBI Research lab ([name])

*Abbreviated Title: Fostamatinib for COVID*

*Version Date: 09/17/2020*

Research (exploratory) 

• Plasma

	2 mL	Sod Citrate (BLU)	D1, 3, 5, 8, 11, 15, 22, 29, 60	NHLBI Research lab ([name])

• PBMC

	9 ml	Sodium Heparin Green top		
Research (exploratory) 

• TEG**

	3mL	Sodium Citrate	D1, 3, 5, 8, 11, 15, 22, 29, 60	NIH Site and Clinical Lab only

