### **Assessment of adverse events:**

Assessment of adverse events will be performed daily by the study team and as clinically indicated. Adverse events that have not resolved after completion of study drug administration will be followed until day 60.

Subjects with LFTs above 3x the ULN at enrollment will have LFTs checked daily during the hospitalization phase of the study.

Subjects who are discharged on study drug will receive a daily phone call until day 15 to assess for adverse events and will have safety labs drawn as per the schedule safety labs schedule on days 3, 5, 8, 11, and 15 as applicable.

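### Before Day 15, daily adverse event calls and safety labs after discharge depend on whether the patient is still taking study drug

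*Combined protocol and SAP*

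**What the plan says.** Four places make outpatient safety follow-up before Day 15 conditional on study drug.

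- Schedule of Activities (section 1.3), footnote f: "Following discharge patients only required to return for day 15, 22, 29, and 60 follow up visits unless they are discharged on study drug". For that exception, "they will receive daily phone calls and will be required to have safety labs drawn as scheduled on days 3, 5, 8, 11".
- Schedule of Activities, heading of the daily column: "Daily until day 15 if discharged on study drug or daily if in hospital until day 60".
- Section 4.1: "Patients who are discharged on study drug will receive a phone call daily to assess for adverse events". The same sentence adds the safety labs and allows a third-party laboratory to draw them.
- Section 8.3, adverse event assessment: "Subjects who are discharged on study drug will receive a daily phone call until day 15 to assess for adverse events". The safety labs follow in the same sentence.

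The table in section 8.2.2 lists routine blood count, chemistry and liver tests as "D1-entire hospitalization, D15, D22, D29, D60 if outpatient". It shows no outpatient draw before Day 15 for anyone, on or off drug.

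Section 7.1 keeps patients who stop drug in the study and says that "remaining study procedures should be completed as indicated by the study protocol".

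Section 8.2 reads differently: "If a subject is discharged prior to Day 15, clinical status is captured on Day 5, 8, 11, 15, 22, 29, and 60". This may be done by phone or telehealth and carries no condition about study drug.

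**The concern.** The trial's main question is comparative safety. Being on or off drug at discharge is decided after randomization, and the drug's own toxicity can change it. Section 6.1.2.3 lists blood pressure, liver, diarrhea and neutrophil findings that interrupt dosing, and section 7.1 says a patient stopped for a safety reason does not resume. Section 2.3.1 lists these same toxicities among reactions seen more often than on placebo.

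So the effort spent looking for events after discharge depends on something treatment may influence. If more fostamatinib than placebo patients go home off drug, fewer calls and draws are made in the fostamatinib arm, and events that only a scheduled contact or test would find are undercounted there. Grade 3 and 4 events through Day 60 are a secondary endpoint, and section 8.4.4 requires clinically significant laboratory abnormalities to be recorded. A raised AST/ALT or a low neutrophil count that appears and resolves between discharge and Day 15 is the clearest example of what could be lost.

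**Working it through.** The plan gives no figure for this point, so there is none to reproduce. The check has three steps.

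**1. Does any other text restore what footnote f removes?**

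- *Daily calls.* Section 8.3 opens with a general statement that the study team assesses adverse events daily. Its only stated mechanism after discharge is the phone call, which is limited to patients on drug.
- *Contacts.* Section 8.2 gives contacts on Days 5, 8 and 11. It defines clinical status by the secondary outcomes, which include Grade 3 and 4 events. Section 9.3.3 determines clinical status from the ordinal scale. Whether these contacts must ask about adverse events is therefore unclear.
- *Safety labs.* Nothing restores them. Section 8.2 can be met by phone. The Schedule's note on outpatient and telehealth visits waives scheduled samples under telehealth unless an outside laboratory can be used. The research draws listed for Days 3 to 11 in section 8.2.2 include no blood count or liver panel.
- *Section 7.1.* It points back to the procedures the protocol indicates, which for a discharged patient off drug are those in footnote f.

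**2. Required contacts strictly before Day 15.**

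For discharge on day d, counting from the next day:

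- Calls on drug = 14 − d.
- Draws on drug = number of Days 3, 5, 8, 11 later than d.
- Section 8.2 contacts = number of Days 5, 8, 11 later than d.
- Gap to the Day 15 visit = 15 − d, or 18 − d if that visit is at the end of the ±3-day outpatient window.

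Day 15 is left out because both groups have a visit then.

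| Discharge day | On drug: calls / draws | Off drug, footnote f: calls / draws | Off drug, section 8.2: contacts | Gap in days (latest) |
|---|---|---|---|---|
| 4 | 10 / 3 | 0 / 0 | 3 | 11 (14) |
| 6 | 8 / 2 | 0 / 0 | 2 | 9 (12) |
| 8 | 6 / 1 | 0 / 0 | 1 | 7 (10) |
| 12 | 2 / 0 | 0 / 0 | 0 | 3 (6) |

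**3. How far could an arm comparison move?**

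This is an illustration; apart from the arm size, none of its inputs comes from the documents. Let f_F and f_P be the shares of the fostamatinib and placebo arms discharged off drug before Day 15, e the risk of a new event in the gap, and m the share of those events missed. Then

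bias in (fostamatinib − placebo) = −m × e × (f_F − f_P).

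Assumed: f_F 10 to 20% with f_P 5 to 10%, f_F always the larger; e 10 to 30%; m 25 to 100%.

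- Low end: 0.25 × 0.10 × (0.10 − 0.05) = 0.00125, about 0.1 percentage points.
- High end: 1.00 × 0.30 × (0.20 − 0.05) = 0.045, or 4.5 percentage points.
- Missed fostamatinib patients out of 30: from 30 × 0.10 × 0.10 × 0.25 = 0.075 (about 0.1) to 30 × 0.20 × 0.30 × 1.00 = 1.8.
- If f_F = f_P, with e and m equal across arms, the bias is 0.

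The high end needs every event in the gap to be missed.

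**The case against.** Three arguments carry weight.

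First, a reader might infer that patients off drug have no adverse event contact at all until Day 15. The documents do not support that. Section 8.2 schedules Days 5, 8 and 11 for everyone discharged before Day 15, the Schedule's note on outpatient visits names the same days without a drug condition, and section 8.3 has its general sentence on daily assessment. Footnote f governs who must return, so a phone capture may even be compatible with it. This argument stands for contacts: the position is unclear and partly contradictory, but contact is not absent. It does not reach the labs.

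Second, a reader might infer that harm is least observed in those who stopped because of toxicity. The event that caused the stop has already been recorded. Sections 8.3, 8.4.3.1 and 8.4.4 follow adverse events after drug ends or until they resolve, and section 8.4.6 does the same for SAEs, whatever the drug status. The off-drug group also includes patients who stopped at their own request or for disease progression. Only new or recurrent events after discharge are sought less.

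Third, closer watching of people taking an investigational drug at home is a reasonable choice, and the rule is the same and blinded in both arms. That is fair as patient oversight, and it means bias arises only if stopping differs by arm. It does not justify collecting trial outcomes on two schedules determined by a post-randomization status.

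**Conclusion.** The point holds as a gap in ascertainment. Before Day 15, safety labs and daily calls after discharge depend on study drug status, and section 8.2 closes only part of the gap. The outcomes exposed are new or recurrent events after discharge, chiefly transient laboratory abnormalities and non-serious Grade 3-4 events.

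The size is unknown. The range of 0.1 to 4.5 percentage points shows only what the assumed inputs imply. The direction, toward understating a fostamatinib excess, also assumes that more fostamatinib patients go home off drug.

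Two further inferences are not supported. One is that the primary comparison is materially biased toward safety. SAEs are recorded from consent through Day 60 regardless of drug status, and the visits on Days 15, 22 and 29 ask about adverse events, readmission and death, so most would be recovered. The other is that the rates in section 2.3.1 (AST/ALT above three times the upper limit in 9%, neutropenia in 6%) estimate the number missed. Their thresholds differ from the stopping criteria in section 6.1.2.3, so they are not stopping rates, and an event that triggers a stop has by definition been seen.

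The change is worth making because it is cheap and removes the dependence on drug status.

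**What to change.** For outcome collection, apply the same adverse event contacts and the Day 3, 5, 8 and 11 safety-lab draws, as applicable, through Day 15 to every patient discharged before Day 15, whether study drug is continuing, on hold or stopped. This means:

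- rewording the condition in footnote f, the Schedule's daily column heading, section 4.1 and section 8.3;
- aligning section 8.2 with them, and stating whether its Day 5, 8 and 11 contacts include adverse event questions;
- adding the outpatient draws before Day 15 to the table in section 8.2.2, which at present omits them even for patients on drug;
- stating how a patient on hold at discharge is classified, which the documents leave open.

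The cost is a wording amendment plus a few extra calls and outpatient draws for those discharged off drug, using the call process and third-party laboratory route already in section 4.1. No dosing, hold or restart rule is proposed.
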